- Occurrence of a medical condition within the exclusion criteria
- Pathologically changed laboratory values in subjects
- Participant becomes pregnant

A final study visit may be conducted for study volunteers who prematurely terminate the study, or for whom the study is discontinued by the DSM. This visit may entail a physical exam and/or laboratory tests as needed to ensure the participant's safety. If the study is discontinued prematurely for any participant because of an SAE, the adverse event will be documented with copies of all associated evaluations and laboratory studies; the investigator must exclude the subject from the study immediately and report the event to the Institutional Review Board and the DSM.

Process of AE/SAE collections, assessing by PI and DSM

The investigators will closely monitor the clinical protocols described in this submission to ensure the safety of volunteers. Subjects will undergo vital sign monitoring throughout the pharmacokinetic study visits as well as pregnancy tests at the screening visit and prior to each administration of dronabinol. Participants will be queried about AEs at all study visits and provided emergency contact information. An AE will be defined as any symptom or abnormal laboratory value that develops or increases in severity during the course of the study and is determined to be clinically relevant.

AEs are recorded at all study visits on dedicated forms and characterized in terms of their start and stop date, maximum intensity, action taken on trial medication, and subject outcome and graded as follows:

Grading of Adverse Events (AEs): AEs will be classified according to severity as below.

Grade 1: A Grade 1 complication is any reported side effect that does not require pharmacologic treatment. An example may be nausea, change in appetite, mild diarrhea or mild infection such as an upper respiratory infection or a headache.

Grade 2: A Grade 2 complication is any that requires pharmacologic treatment. These include minor conditions requiring treatment (e.g. a headache requiring medication).

Grade 3: A Grade 3 complication is one that requires surgical, endoscopic, or radiologic intervention. Grade 3a indicates that the intervention does not require general anesthesia, whereas intervention for a Grade 3b complication requires general anesthesia.

Grade 4: A Grade 4 complication is any life-threatening complication that requires ICU level care. This may involve single organ dysfunction (e.g. dialysis, Grade 4a) or multi-organ dysfunction (Grade 4b).

Grade 5: Death of a patient.

Study investigators will monitor side effects and AEs at the study visits and the recording and reporting of all AEs will be as described above.

If a subject discontinues the trial because of an AE, this is also noted on the AE form. In the event of an SAE (grade 3 or higher), study investigators will complete and submit an Adverse Event Report form to our local IRB and the DSM (see below) within 24 hours of learning of the SAE. In addition, written summaries of the study status will be submitted to the local IRB and NIDA on a yearly basis, or more frequently if requested. Screening laboratory results are reviewed and signed by one of the study physicians on receipt from the clinical laboratory. Our clinical trial may be stopped if emerging effects demonstrate that the volunteers are at risk of SAEs from the study procedures.

8. Trial efficacy

Not Applicable. This study is not a Phase 3 efficacy trial and does not aim to assess efficacy or safety of a medication or device.

9. Administration of DSM Plan

The data and safety monitoring plan (DSMP) will be the responsibility of the study physicians Drs. [name] and [name] who will work closely with [name], PhD (Study PI), to ensure completeness of the DSMP. These individuals will closely monitor the clinical protocols described to ensure the safety of volunteers. When an individual subject completes the study, [name] will review the AE reporting and the study record for that subject. All adverse events, study enrollment and any relevant findings will be reported to the local IRB annually.

A detailed DSM report will be submitted to NIDA annually that includes a description of study progress, enrollment updates, retention and disposition of participants, AE and SAE listings and any regulatory issues such as amendments, protocol deviations, IRB reports and QA issues.

An independent DSM, [name], who is without conflicts of interest with regards to the study or the study investigators, will perform biannual reviews of this study.

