Procedures entail administration of medications, collection of blood and urine, buccal swab for genotyping analyses, and pharmacologic biomarker analysis. Subjects fulfilling eligibility criteria and providing informed consent at the screening visit (study visit 1) will arrive to the UW ITHS Adult Translational Research Unit (TRU) for each of the 4 study visits: twice before (study visits 2 and 6; pre-hormone treatment control days) and twice after sequential treatment with estradiol and cortisol (study visits 4 and 8; post-hormone treatment days). A baseline blood draw (time 0 hr) will be performed (24 mL of blood) to establish baseline levels of cortisol and estradiol and collect peripheral blood mononuclear cells (PBMCs). At the pre-treatment pharmacokinetic study visits, subjects will take a single dose of dronabinol (2.5 mg PO). The subjects will then collect their urine for 24 hours. Additionally, after placement of an intravenous catheter, venous blood samples (2-4 mL per time point) will be collected at 0.5, 1, 1.5, 2, 3, 4, 6, 8, 10, 12 and 24 hours after THC dosing. The total volume of blood drawn will not exceed 75 mL. At each time point, pharmacological biomarker analysis will also be performed. Heart rate changes will be recorded as an objective measure of pharmacologic effects of dronabinol. At each time point, participants will also complete a questionnaire describing subjective effects related to mood, drug effect, and physical symptoms using a visual analog scale (VAS). After a minimum washout period of one week, the subject will have an estradiol patch applied for one week, delivering 0.3 mg/day or take hydrocortisone twice daily by mouth (30 mg/day; 20 mg in the morning and 10 mg in the afternoon) for one week prior to returning to the clinic for the post-treatment pharmacokinetic study visits. Dronabinol dosing, urine and blood sampling, and pharmacological analysis will be identical to that performed on the first study visit. Subjects will leave the TRU after the 12-hour timepoint for each pharmacokinetic study and present to the Center for Research in Reproduction and

Contraception (CRRC) for a study visit the following morning (study visits 3, 5, 7, and 9) to return the 24-hour urine collection and undergo blood sampling at the 24-hour timepoint.

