Participants will be randomized for drug treatment order (e.g. whether they will undergo treatment with estradiol or hydrocortisone first). All study participants will undergo both drug treatments.

Table of Study Events

Procedure	Screening	Pre-treatment PK study, day 1	Pre-treatment PK study, day 2	Post-treatment PK study, day 1	Post-treatment PK study, day 2
Room #	Visit 1 CRRC	Visits 2, 6* ITHS Adult TRU	Visits 3, 7* CRRC	Visits 4, 8* ITHS Adult CRU	Visits 5, 9* CRRC
		Baseline: prior to estradiol or hydrocortisone treatment		After 1 week of estradiol or hydrocortisone treatment	
Consent/HIPAA	X				
Medical History	X				
Body weight and vital signs	X	X		X	
Physical exam	X				
Buccal swab for DNA testing	X				
Dronabinol administration		X		X	
IV catheter placement and blood draws over 12 hours		X		X	
Non-fasting blood draw	X		X		X
Urine pregnancy test	X	X		X	
Begin 24-hour urine collection		X		X	
Drug dispensing** (estradiol or hydrocortisone)			X		
Adverse event query		X	X	X	X
Payment	\$50	\$200		\$200	

*Parallel visits (6, 7, 8, and 9) will occur after the second drug treatment period.
 
**Participants will complete 7 days of treatment with either estradiol or hydrocortisone immediately following Visit 3 and Visit 7.
 
PK = pharmacokinetic
 
Pre-treatment PK visits will be scheduled on menstrual cycle days 0-3 for hydrocortisone and 15-17 for estradiol
 
An additional \$150 will be paid upon study completion for a total compensation of \$1,000
					

Primary and Secondary Objectives and outcome measures

The goal of this aim is to test *in vivo* in women the hypothesis that increased concentrations of estradiol and/or cortisol lead to increased metabolic clearance of THC. The rationale is to specifically isolate the influence of pregnancy hormones in regulating CYP-mediated THC clearance in the absence of other complicating physiological changes that occur during pregnancy. This study is unique as, unlike studies done during pregnancy that demonstrate associations, **this study will test causality**. It will specifically test whether the pregnancy hormones commonly implicated in pregnancy-mediated regulation of CYP enzymes cause an induction of CYP activity *in vivo*. The obtained data will be **critical** for developing an understanding of how THC disposition varies between individuals and in predicting how the exposures to THC and its metabolites might be altered during pregnancy

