The primary outcome is to determine whether exposure to THC (as determined by AUC) is altered consequent to hydrocortisone treatment when compared to the pre-treatment control and to quantify the magnitude of the change.

Secondary Outcome 1: Determination of whether other pharmacokinetic parameters of THC and its metabolites are different as a consequence of hydrocortisone treatment

We will determine the time to peak concentration of THC, the peak concentration of THC, and the half-life of THC before and after estradiol treatment. We will also determine the AUC of metabolites of THC (11-OH-THC, 11-nor-COOH-THC, the glucuronides of 11-OH-THC and 11-nor-COOH-THC) before and after hydrocortisone treatment. We will calculate the fraction of THC dose excreted into urine in the form of each of the metabolites and the renal clearance of each of the compounds based on urine and plasma data.

Secondary Outcome 2: Determination of the magnitude of effect of THC on heart rate in the presence and absence of hydrocortisone treatment

As an objective measure of the pharmacologic effects of dronabinol, subjects will undergo monitoring of heart rate. The change in heart rate will be reported for each time point after dosing in comparison to baseline. The time course of change in heart rate will be reported and the change in heart rate at each time point after baseline will be compared to baseline. These data will be used as a descriptive measure of the magnitude and duration of the pharmacological effects of THC and to explore whether the doses used are pharmacologically active.

Secondary Outcome 3: Description of the psychoactive effects and side effects caused by THC in the presence and absence of hydrocortisone treatment

Subjects will be asked to rate subjective effects related to mood, drug effect, and physical symptoms using a VAS as a function of time after dronabinol dosing. Subjects will complete VAS ratings at each of the blood sampling timepoints during the pharmacokinetic study visits.

Inclusion and Exclusion Criteria:

Inclusion Criteria

- a. Healthy, premenopausal women ages 21-45 years old
- b. Normal menstrual cycles (monthly, cycles 28-35 days in length)
- c. Body mass index $<30 \text{ kg/m}^2$
- d. Must be willing to use nonhormonal methods to avoid conception during the study period

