Dronabinol oral capsule is commonly administered to patients with loss of appetite. The recommended dose of dronabinol oral capsule is 2.5 mg twice daily. The dose may be reduced to 2.5 mg once daily for patients who are unable to tolerate higher doses. The dose may also be increased gradually based on response and tolerability. Treatment in this study is short-term (single dose). Short-term adverse events that can occur at a higher incidence than placebo include confusion, increased appetite, nausea and asthenia. Risks of these side effects are minimized by using the lowest clinically approved dose which adheres to the recommended dosage form: 2.5 mg once daily.

Estradiol patches are mainly used clinically in postmenopausal women with a typical replacement dose of 0.025-0.1 mg/24 hr. We expect transdermal estradiol at the administered dose (0.3 mg/24 hr) to increase circulating estradiol levels by ~200-280 pg/mL. Luteal phase estradiol levels can vary widely, from about 50-200 pg/mL. Thus, we anticipate that treatment will at least double estradiol exposure in most participants to ~250-480 pg/mL. This change in estradiol is the minimum needed to model the effects of estradiol on THC metabolism during pregnancy, when estradiol levels may reach 5,000-7,000 pg/mL. The risks of exogenous estrogens include increased risk of blood clots, elevations in blood pressure and plasma triglycerides, and increased risk of breast cancer and stroke in older women. Transdermal estradiol is the safest form of exogenous estradiol, and the risks of week-long dosing in pre-menopausal women are minimal. Nevertheless, as a conservative approach, we will exclude potential subjects with a history of blood clots, uncontrolled hypertension, moderate-severe hypertriglyceridemia, or a personal or family history of breast or ovarian cancer in a first degree relative. Short-term adverse events that can occur at a higher incidence than placebo include rashes, edema and elevated triglycerides. The subjects may also experience gastrointestinal changes and irritation, mood and sleep changes, headaches, hypertension, application site reaction, nausea, breast tenderness/swelling, changes in menstrual flow or cycle and leg cramps.

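### The procedures text and the Table of Study Events give conflicting start times for the hormone course; following the procedures text would move some estradiol-phase treated visits into the next menstrual cycle

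*Combined protocol and SAP*

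**What the plan says.** Section 2, Summary of the Protocol, describes the control dronabinol visit and continues: "After a minimum washout period of one week, the subject will have an estradiol patch applied for one week". Hydrocortisone for a week is given as the alternative, in either case "for one week prior to returning to the clinic for the post-treatment pharmacokinetic study visits". The washout is a minimum only.

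The Table of Study Events dispenses the hormone at Visits 3 and 7, which are the morning after the control dose. Its footnote reads: "Participants will complete 7 days of treatment with either estradiol or hydrocortisone immediately following Visit 3 and Visit 7". The treated visits (4 and 8) are headed "After 1 week of estradiol or hydrocortisone treatment".

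Control visits are tied to the cycle: "Pre-treatment PK visits will be scheduled on menstrual cycle days 0-3 for hydrocortisone and 15-17 for estradiol". Treated visits have no cycle-day window. Eligible women have cycles of 28 to 35 days (Inclusion Criteria).

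Section 7, Potential Risks, justifies the patch dose from a luteal baseline: "Luteal phase estradiol levels can vary widely, from about 50-200 pg/mL". It expects that "treatment will at least double estradiol exposure in most participants to ~250-480 pg/mL".

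**The concern.** A course that begins the morning after the control dose leaves no room for a week of washout before it. Because only control visits are fixed by cycle day, the start rule alone decides the cycle day of the treated visit.

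This bears on the primary comparison. Each woman is her own control, and the estradiol dose was chosen to add to her own luteal estradiol. If she has passed into her next cycle by the treated visit, the patch partly replaces estradiol she has lost. If estradiol induces THC clearance, as the study hypothesises, her AUC ratio then moves toward 1.

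In the hydrocortisone phase the later start moves the treated visit from the first part of the cycle to around mid-cycle. Her own estradiol, the study's other candidate inducer, may then differ more from control. The documents give no figure for that, and control and treated cycle days differ under either rule.

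**Working it through.** **Plan's own figure.** Luteal 50-200 pg/mL plus a patch rise of 200-280 pg/mL gives 50 + 200 = 250 to 200 + 280 = 480 pg/mL. This reproduces the range in section 7. It needs a luteal background at the treated visit.

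**Timing.** Treated day = control day + 1 + 7 under the footnote, or control day + washout (at least 7) + 7 under the procedures text. Control days are 15-17 (estradiol) and 0-3 (hydrocortisone).

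| Rule | Control to treated | Estradiol treated day | Hydrocortisone treated day | Estradiol combinations in next cycle |
|---|---|---|---|---|
| Footnote | +8 | 23-25 | 8-11 | 0 of 24 |
| Procedures text, 7-day washout | +14 | 29-31 | 14-17 | 6 of 24 (9 of 24) |
| Procedures text, 14-day washout | +21 | 36-38 | 21-24 | 24 of 24 |

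The grid is 8 cycle lengths (28-35) by 3 control days. At +14, if menses starts on day 1, the count is 3 for 28-day cycles, 2 for 29-day and 1 for 30-day: 3 + 2 + 1 = 6. If menses starts on day 0, which the day 0-3 window suggests, it is 3 + 3 + 2 + 1 = 9 (figure in brackets). If the washout is counted from Visit 3/7, the interval is +15 and the count is 9 to 12.

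**Size of the bias (assumed model, not in the documents).** Control estradiol 50-200, patch rise 200-280 and own estradiol at menses 20-60 pg/mL, all uniform; induction proportional to the estradiol rise.

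- A woman fully at menses level keeps (menses + patch − control)/patch of the planned rise. The mean is 0.64, so the mean deficit is 0.36.
- Section 2 predicts 50% induction of clearance, so the planned ratio is 1/1.5 = 0.667. With share s of the rise kept, the ratio is 1/(1 + 0.5s). A full deficit in every woman gives a geometric mean of 0.759, the upper limit in this model.
- Enzyme activity does not fall at once. With half-life h, the part of the deficit expressed t hours after estradiol falls is 1 − 2^(−t/h). I took h = 24 to 96 h.

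Example at +14, day-1 numbering, h = 24 h, fall at menses: of the 6 shifted combinations, 3 are on the first day of the new cycle (t = 0), 2 on the second (24 h) and 1 on the third (48 h). The expressed parts are 0, 0.5 and 0.75. With mean deficit 0.357, s is 1, 0.821 and 0.732, and the ratios are 0.667, 0.709 and 0.732. Averaging logs over the grid: [21 × (−0.4055) + 2 × (−0.3440) + (−0.3119)]/24 = −0.396, a ratio of 0.673.

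| Washout 7 days (+14) | Day-1 numbering | Day-0 numbering |
|---|---|---|
| Estradiol falls at menses, h = 96 to 24 h | 0.669-0.673 | 0.672-0.680 |
| Falls two days earlier, h = 96 to 48 h | 0.676-0.682 | 0.681-0.690 |
| Falls two days earlier, h = 24 h | 0.690 | 0.700 |

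In the last two rows, women within two days of menses also lose some of the rise. At +21, with the fall at menses, the same formula over all 24 combinations gives about 0.71 to 0.75.

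**The case against.** The strongest reply is that the documents already point to one schedule. Section 2 refers the reader to the Table of Study Events for the visits, the table dispenses hormone at Visits 3 and 7, and the dose rationale assumes a luteal background. Under that schedule no combination shifts and nothing is lost. This stands as evidence of intent. It does not remove the other clause, which staff could follow as written.

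A second reply is that washout means the gap between dronabinol doses, which the seven-day course fills. That may be what was meant, but the sentence puts the washout before the patch or tablets.

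Third, hormone concentrations are measured at each visit, so a failed rise would be seen. That is true, but only after the visit has been spent.

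A reader might infer that a quarter or more of the women would be tested in the wrong cycle, or that power would drop materially. The documents support neither. The counts give every cycle length and control day equal weight; they do not predict who enrols. A large loss at the minimum washout appears only if each shifted woman is treated as having spent her whole patch week at menses level, when most of that week falls in the old cycle. The plan also states no standard deviation, so any power figure would rest on a back-solved one.

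**Conclusion.** The conflict is real and needs no model: the two start rules are incompatible, and they place the treated visit at about +8 days or at +14 days or later. The footnote is very probably the intended rule. If the procedures text were followed at its minimum washout, 6 to 9 of 24 estradiol-phase combinations would cross into the next cycle. The expected AUC ratio would move from 0.667 to about 0.67-0.68, or up to about 0.70 if estradiol falls before menses and induction fades quickly. That is a small bias toward no effect. It grows with longer washouts, which the text does not prevent; at two weeks all 24 combinations cross over.

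The sizes rest on assumed menses estradiol, induction proportional to the estradiol rise, assumed half-lives, and cycle length unchanged by the patch. The hydrocortisone consequence is not quantified. This is a wrong clause worth correcting, not evidence that the estradiol comparison fails.

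**What to change.** Replace the washout clause in section 2 with wording such as: *The 7-day hormone course starts after the 24-h draw at Visit 3/7, and dronabinol is given at Visit 4/8 on completion of the 7 days (about 8 days after the control dose). At least one week separates any two dronabinol doses.* Record cycle day at every pharmacokinetic visit.

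The second sentence keeps the one-week minimum but ties it to dronabinol. Between control and treated visits it is met by design. It also covers Visit 4 to Visit 6, where the cycle-day rule alone allows 15 − 11 = 4 days (hydrocortisone first) or, in a 28-day cycle with menses on day 0, 28 − 25 = 3 days (estradiol first).

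The cost is one wording amendment, which needs NIDA approval under section 6, and one recorded item per pharmacokinetic visit. The hormone course stays at seven days, with no added visits, blood or subjects. A few women may wait a cycle for Visit 6.

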1. PrCEPT Study Protocol and Analysis Plan

Funding: P01 DA032507-06A1 Pharmacology of Drugs of Abuse in Pregnancy

Title: Effects of Pregnancy-associated Hormones on THC Metabolism in Women

NCT number: NCT04374773

Project principal Investigator: [name]

2. Summary of the Protocol

Description of the protocol, procedures and table of events:

The clinical study will be conducted to investigate the induction of cannabis metabolism by estradiol and glucocorticoid (hydrocortisone) hormone treatment (Table 1). We have chosen to use hydrocortisone to mimic endogenous cortisol increase as observed in pregnancy instead of synthetic corticosteroid, as hydrocortisone is the most commonly used corticosteroid for physiologic replacement in clinical practice. We intend to study THC metabolism in enrolled subjects following administration of dronabinol once before (study visits 2 and 6; pre-hormone treatment control day; please see Table of Study Events below) and once after sequential estradiol and cortisol treatment (study visits 4 and 8; post-hormone treatment). During each visit, investigators will collect serial blood and urine samples to measure THC, THC metabolite, and hormone concentrations. Additionally, biomarker-based assessment of THC pharmacologic effects will be accomplished through measurement of heart rate and subject rating of side effects and psychoactive effects using a visual analog scale (VAS).

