Table 2. Planned Enrollment table. We anticipate initiation of participant recruitment and enrollment roughly midway through Year 1, and we plan to complete enrollment during Year 4. All subjects will undergo sequential treatment with estradiol and hydrocortisone, with pre- and post-treatment doses of dronabinol for each hormone exposure. Subjects will be randomized to treatment order.

Grant year	Number of subjects enrolled during the year	Cumulative number of subjects enrolled
Year 1	3	3
Year 2	4	7
Year 3	5	12
Year 4	4	16
Year 5	0	16

Healthy, 21-45-year-old premenopausal, non-pregnant female volunteers will be enrolled to complete the study. Since the research is focused specifically on THC exposure during pregnancy, only women will be enrolled in the study. In addition, estradiol is approved for use only in women. Dronabinol is only approved for use in adults. Therefore, we will not recruit individuals under the age of 21. At present the psychological and developmental risks of dronabinol use in children are unknown.

We ask study subjects to volunteer information about their race and ethnicity, but this information is not required for participation in our studies. Our previous clinical research studies have had the following demographic distribution: 85% of our study subjects are Caucasian, 5% are African-American, 7.5% are Asian and 1% each Native American and Hispanic. This breakdown closely reflects the demographics of our community, and we remain committed to increasing enrollment of underrepresented minorities in our studies.

4. Data Management

Statistical analysis plan

The changes in AUC of THC after treatment with either estradiol or hydrocortisone will be tested using paired analysis of variance on log-transformed data with each subject serving as her own control. Point estimates and 90% confidence intervals will be defined for treatment versus control in THC disposition in accordance to the guidance on statistical analysis of DDI studies. To establish a difference between treatment and control, % confidence interval of the geometric means must be outside of the range of 0.80 to 1.25. This statistical analysis is concordant with the FDA guidance on analysis of drug-drug interaction data.

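### Hydrocortisone control and treated visits fall on different menstrual cycle days, so natural estradiol change can bias the THC AUC ratio, and the analysis leaves the measured estradiol unused

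*Combined protocol and SAP*

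**What the plan says.** The footnote to the Table of Study Events fixes the control visits only: "Pre-treatment PK visits will be scheduled on menstrual cycle days 0-3 for hydrocortisone and 15-17 for estradiol". No cycle day is given for the treated visits, and the documents give two different intervals to them. The same table says "Participants will complete 7 days of treatment with either estradiol or hydrocortisone immediately following Visit 3 and Visit 7". The Summary of the Protocol (section 2) says "After a minimum washout period of one week, the subject will have an estradiol patch applied for one week", with one week of oral hydrocortisone as the alternative.

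Randomisation covers the order of the two hormones. Within each phase the control visit always precedes the treated visit. Eligible women have "Normal menstrual cycles (monthly, cycles 28-35 days in length".

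The stated hypothesis is that estradiol, cortisol or both raise THC clearance, and the objectives text adds that "this study will test causality". At each visit "investigators will collect serial blood and urine samples to measure THC, THC metabolite, and hormone concentrations", and a time-0 draw establishes baseline estradiol and cortisol. The Statistical analysis plan (section 4) tests the AUC change by "paired analysis of variance on log-transformed data with each subject serving as her own control". It names no estradiol, cycle-day, period or order term, and cycle day is nowhere listed as a limitation.

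**The concern.** Pairing removes differences between women. It does not remove what changes within a woman between two cycle days. For hydrocortisone, the quantity likely to change is estradiol, the other hormone that the trial expects to induce THC clearance. A natural estradiol rise between the visits would lower THC AUC under the trial's own hypothesis and be credited to hydrocortisone. Randomising hormone order does not help, because cycle day is tied to the hormone and control is always first.

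The primary outcome in each phase is both to detect a change and to quantify it. A biased ratio fails the second aim whether or not a difference is declared. The data needed to examine the bias are already collected.

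**Working it through.** **1. Cycle days.** Start from the control days in the table footnote.
- Table footnote (7 days of treatment straight after the 24-hour visit): add about 8 or 9 days. Hydrocortisone: 0+8 to 3+9, days 8-12. Estradiol: 15+8 to 17+9, days 23-26.
- Section 2 text (at least one week of washout, then one week of treatment): add at least 14 days. Hydrocortisone: days 14-17 or later. Estradiol: days 29-31 or later.

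Under either reading the treated visit is at least 8 days later in time than its control.

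**2. The plan's sample size.** The target is 12 completers per phase for 80% power, alpha 5% and a 25% AUC decrease. The SD is not given, so 12 cannot be checked, only solved backwards. A two-sided paired t-test on log AUC with n = 12 and effect ln 0.75 = -0.288 has 80% power when the SD of the paired log difference is 0.324. Then SE = 0.324/√12 = 0.0935 with 11 df.

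**3. Anchor for the bias.** Section 7 gives luteal estradiol of about 50-200 pg/mL, a patch increment of about 200-280 pg/mL, and resulting levels of about 250-480 pg/mL. The implied fold rise F runs from 480/200 = 2.4 to 250/50 = 5. Assume that F produces the planned ratio of 0.75 and that log AUC is linear in log estradiol. With no hydrocortisone effect and a natural rise of f-fold:

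apparent ratio = 0.75^(ln f / ln F)

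The values of f are assumptions, because no menstrual or follicular estradiol level is given.

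| Natural rise f | Apparent ratio, F = 2.4 | Apparent ratio, F = 5 | Paired 5% test rejects |
|---|---|---|---|
| 1.25 | 0.929 | 0.961 | 7-11% |
| 1.5 | 0.875 | 0.930 | 11-26% |
| 2 | 0.796 | 0.883 | 23-60% |

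Rejection probabilities are noncentral t with 11 df and SE 0.0935. Example for f = 2, F = 2.4: ln 2/ln 2.4 = 0.792, and 0.75^0.792 = 0.796.

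On an additive scale the bias is usually smaller. The ratio is 0.75^(rise/increment), so assumed natural rises of 25 to 150 pg/mL against 200-280 pg/mL give 0.975 (25/280) to 0.806 (150/200).

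**4. The plan's decision rule.** The plan reports 90% intervals and refers to the range 0.80 to 1.25. If a decrease is declared only when the whole 90% interval lies below 0.80, the probability under no hydrocortisone effect is 0.4% at a ratio of 0.883 and 5.5% at 0.796. It is lower for the smaller natural rises.

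**5. Effect on the estimate.** The bias multiplies the true ratio. With a true ratio of 0.75 and a natural doubling, the trial would on average report 0.75 × 0.883 = 0.66 to 0.75 × 0.796 = 0.60.

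**6. Can adjustment work at n = 12?**
- Adding the change in log estradiol to the 12 hydrocortisone pairs alone multiplies the SE by √(1 + (12/11)m²/s²), where m and s are the mean and SD of that change. For m = ln 2 and s = 0.7 to 0.3, the multiplier is 1.44 to 2.61, and power at 0.75 falls from 80% to between 49% and 19%.
- A model on all four log AUCs per woman also uses the large patch-induced change. It was simulated with n = 12, paired SD 0.324, the section 7 luteal and patch ranges, an assumed control estradiol of about 50 pg/mL on days 0-3, and natural rises of 1.25- to 3-fold. It gave about 5% rejection with no hydrocortisone effect. At a true ratio of 0.75 the estimate was 0.75 with 92-96% power, and the SE was about 0.08 against 0.094 for the paired test. These figures hold only if the model's assumptions hold.

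**The case against.** Several stronger readings are tempting, and the documents do not support them.

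- A reader might infer that the paired visits fall in different menstrual phases. Assume ovulation 14 days before the next menses, so day 14 to 21 for 28- to 35-day cycles. Under the table footnote both hydrocortisone visits then precede ovulation, and in a 28-day cycle both estradiol visits follow it. A phase change needs the section 2 washout or, for the estradiol pair, a longer cycle. Different cycle days is what is shown.
- A reader might take the statement that "treatment will at least double estradiol exposure in most participants" to mean that a doubling produces the design effect. Natural rises of 1.25-, 1.5- and 2-fold would then give ratios of 0.91, 0.85 and 0.75, with 15%, 38% and 80% rejection. But doubling is a floor there, the levels given imply 2.4- to 5-fold, and the 25% AUC decrease is not linked to a doubling.
- A reader might infer frequent false claims from the paired 5% test. The plan's stated criterion is the interval rule, under which they are uncommon.

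Against the remedy: the four-visit model assumes that patch and natural estradiol act alike on one log-linear line. Estradiol at the treated hydrocortisone visit is also measured after a week of hydrocortisone; if hydrocortisone shifts it, adjustment removes part of the effect under study. Both points stand. They rule out making attribution to hydrocortisone conditional on the adjusted model, but not a sensitivity analysis.

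The causality sentence can be read as rationale, contrasting an intervention with observational pregnancy studies. That is fair, so the qualification belongs on the hydrocortisone conclusion and only if the analyses disagree.

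**Conclusion.** The point holds for the hydrocortisone contrast. Control and treated visits differ in cycle day by design, randomisation does not balance this, and the planned analysis cannot separate natural estradiol change from hydrocortisone.

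The size cannot be fixed from the documents. Under the 2.4- to 5-fold log-linear anchor, an assumed natural doubling gives an apparent ratio of 0.80-0.88 with no true effect; smaller rises or an additive scale generally give less. If estradiol instead fell between the visits, the bias would run the other way. The main harm is a biased estimate of magnitude. The 5.5% ceiling on false claims applies to rises up to 2-fold, no true effect, SD 0.324, and the whole-interval reading of the rule. The sample size of 12 is not shown to be wrong.

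**What to change.** 1. Pre-specify, beside the primary paired result, a sensitivity mixed model on all four log AUCs per woman, with a random subject effect, a hydrocortisone term and log time-0 serum estradiol. State its assumptions: a log-linear relation, patch and natural estradiol acting alike, and no effect of hydrocortisone on estradiol.
2. Report the within-woman contrast of the two control days (15-17 versus 0-3) as a descriptive estimate of the cycle effect. It nearly matches the earliest hydrocortisone treated days under the section 2 timing (14-17), but not under the table footnote (8-12).
3. State that the causal conclusion for hydrocortisone will be qualified if the paired and sensitivity results disagree.
4. Reconcile the one-week washout in section 2 with the immediate start of treatment in the table footnote, and state the resulting cycle days of the treated visits.

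The cost is SAP text and one extra model; no new visit, sample or participant is needed. The model brings assumptions that the trial can test only weakly, and it does not remove any time-order effect from control always coming first.
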